### **Sample size justification:**

#### Statistical Hypothesis:

Null hypothesis: Treatment of melasma on face with Clear & Brilliant laser and topical cysteamine will not lead to significant improvement

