#### **Background:**

Melasma is a commonly acquired hyperpigmentary condition characterized by brown spots on sun exposed areas of the face. Treatment of melasma can be challenging as many patients are refractory to therapy, while others experience a chronic or relapsing course. Melasma also significantly impact patients' quality of life with many reporting feelings of frustration, embarrassment, and depression related to their condition. Mainstay of treatment includes topical skin-lightening and brightening agents such as hydroquinone, tranexamic acid, retinoids, azelaic, kojic and ascorbic acids, as well as various chemical peels, laser and light-based therapies. Current gold standard is a triple combination cream consisting of topical hydroquinone, tretinoin, and fluocinolone, along with broad-spectrum sunscreen. However, use of topical hydroquinone is associated with adverse events including irritation and a paradoxical exogenous ochronosis with prolonged use, making its use challenging. Hence, for this difficult, and often recalcitrant disease, additional therapeutic options are needed.

Topical cysteamine is safe, generally well tolerated, and can be used continuously without treatment holidays. Multiple studies have demonstrated its efficacy in the treatment of melasma, including two double-blind, randomized, and placebo controlled clinical trials. Combination therapy of lasers with lightening agents have been shown to augment melasma treatment. However, data on combination laser and topical cysteamine is sparse, and no controlled or split-faced studies have been published. Thus, we aim to investigate combined topical cysteamine with laser, compared with topical cysteamine alone to assess whether this adjuvant therapy can improve the efficacy of cysteamine in the treatment of melasma.

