The primary objective of our study is to determine the efficacy of combined topical cysteamine cream with a 1927 diode non-ablative laser (Clear + Brilliant Permea®; Solta Medical, Inc.), compared to topical cysteamine alone in the treatment of melasma. This efficacy will be assessed using modified Melasma Area and Severity Index (mMASI) scores, a validated physician assessment tool, at baseline and at follow up visits at week 4, 8 and 12 as well as Investigator Global Assessments. Secondary objectives also include an assessment of patient satisfaction which will be evaluated via patient questionnaires distributed to patients at baseline and at week 12. In addition, impact on quality of life will also be assessed utilizing the melasma quality of life scale (MELASQoL) questionnaire which will be administered to patients at baseline and at week 12.

Multiple studies have demonstrated the efficacy of topical cysteamine in the treatment of melasma. Mansouri et al. conducted a double-blind, randomized, controlled clinical study, which included 50 melasma patients, and demonstrated significant efficacy of topical cysteamine in the treatment of melasma. One comparative trial demonstrated that topical 5% cysteamine, though safe and well-tolerated, was less effective than topical 4% hydroquinone in the treatment of facial melasma; however, a later published response indicated that the concentration of cysteamine may have been less than the reported 5%. A single-blind, randomized comparative trial of 54 melasma patients found no statistically significant difference in the efficacy of topical cysteamine compared to topical tranexamic acid; however, cysteamine was better tolerated amongst the patients. Finally, Karrabi et al. also found that cysteamine 5% cream showed greater efficacy than the gold standard, modified Kligman's formula, in their randomized, double-blind trial of 50 patients with epidermal melasma.

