We hypothesize that addition of 1927-nm fractional low-powered diode laser therapy to topical 5% cysteamine will result in significantly greater improvement in both the clinical appearance of melasma as well as patient satisfaction, compared to topical cysteamine alone. Specifically, we hypothesize:

- 1) Patients will experience improvement in their melasma on both treated sides, with greater improvement noted with combined topical and 1927-nm fractional low-powered diode laser treatment noted on their mMASI scores at weeks 4, 8 and 12.
- 2) Patients will report improvement in satisfaction on patient questionnaires on both treated sides, however there will be greater change in satisfaction noted with combined topical and 1927-nm fractional low-powered diode laser treatment at week 12 compared to baseline (week 0)

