**Objectives:**

- A. To evaluate the efficacy of the Clear & Brilliant Permea laser system in combination with topical cysteamine
  - a. To assess for improvement of melasma after completion of three treatments as determined by the treating clinician and objective measures
  - b. To evaluate subject's satisfaction with melasma treatment and assessment of improvement after three treatments
  - c. To evaluate the length of treatment.
- B. To evaluate the safety of melasma treatment in all skin types using the Clear & Brilliant Permea laser in combination with topical cysteamine
  - a. To evaluate the immediate response to treatment
  - b. To evaluate the subject's assessment of comfort associated with treatments
  - c. To determine the rate of adverse events for the treatment group as a whole

**Study Design:** Single Center, Prospective, With Before-After Analysis

**Study population:** Twenty healthy male or female patients, 18-74 years of age, of all skin types with melasma on the face that wish to be treated. Each subject will receive topical cysteamine cream which they will be instructed to use once a day at home. In addition, one side of the face will be randomly selected for treatment with laser. Patients will receive three monthly treatments, at 4-6 week intervals, on the selected side of the face with the Clear & Brilliant Permea laser. The treatment duration including pre and post treatment procedures is estimated to be 90 minutes per subject. Subjects will return for a follow-up visit 3 months after the initial treatment for a total of four visits. The treatment plan will be the same regardless of the subject's skin type. Four passes, at high setting will be performed.

During the first and fourth visit, the areas of treatment will be photographed with a digital camera under controlled conditions. Subject improvement will be assessed via investigator and subject grading at visit 1 and 4. Improvement in melasma will be assessed by blinded evaluators who will review pre and post treatment photographs taken with VISIA® Skin Analysis System for facial imaging (Canfield Scientific Inc) from visit 1 and 4. Side effects (including pain, redness, dryness, and hyperpigmentation) will be assessed and recorded at visits 2, 3, 4.

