#### Sample Size Calculation:

A sample size is calculated to test the null hypothesis with a one-sided paired t-test for simplicity, although the final analysis may employ a statistically more powerful model.

We calculate that for a two-sided alpha level of 5%, a sample size of 20 subjects will enable us to test the null hypothesis with 80% power. In order to enable the analysis and take into account the potential for dropout we may include up to 25 patients.

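### The only formal null hypothesis names no comparator, and the pairing, design label and mMASI endpoint do not supply one, although the objective and the randomised split face compare laser plus cysteamine with cysteamine alone

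*Protocol*

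**What the plan says.** Under Statistical Hypothesis the protocol gives a single null: "Treatment of melasma on face with Clear & Brilliant laser and topical cysteamine will not lead to significant improvement". Under Sample Size Calculation it continues: "A sample size is calculated to test the null hypothesis with a one-sided paired t-test for simplicity". It then states, for a two-sided 5% level, that "a sample size of 20 subjects will enable us to test the null hypothesis with 80% power". Up to 25 patients may be included to allow for dropout. Neither section names a comparator or says which two measurements form the pair.

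The Study Design line reads "Single Center, Prospective, With Before-After Analysis". Under Criteria of Evaluation, the in-person endpoint is the change in mMASI of the subject's face from baseline to week 4, with no contrast between sides.

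Other parts of the protocol are comparative:

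- The Background gives the aim as the combination "compared with topical cysteamine alone to assess whether this adjuvant therapy can improve the efficacy of cysteamine".
- The primary objective sets the combination against the cream: "compared to topical cysteamine alone in the treatment of melasma".
- The first research hypothesis begins "Patients will experience improvement in their melasma on both treated sides" and goes on to predict more improvement on the combined side.
- Under Study population every subject uses cysteamine, and "one side of the face will be randomly selected for treatment with laser".

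**The concern.** Rejecting a null should support the primary objective. This null, read literally, concerns improvement under the combination, not improvement beyond cysteamine. The protocol itself expects both sides to improve, so it expects the literal null to be false even if the laser does nothing. A significant result could then be reported as success for the combination when cysteamine produced all of it.

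The whole-face endpoint adds to the problem. A total mMASI is one score per patient per visit and pools the laser side with the untreated side. A paired test on that total can only compare visits. It cannot compare sides.

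The wording also leaves open which result counts as success, and that choice could be made after the data are seen.

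**Working it through.** **1. The plan's own figure.** The protocol gives no effect size and no SD, so 20 subjects cannot be reproduced. It can be inverted. For a paired t-test with n pairs and a true mean difference of d SDs of the paired differences, the statistic follows a noncentral t with n − 1 degrees of freedom and noncentrality d√n. Two-sided power is the probability that it falls beyond ±t(0.975, n − 1); one-sided power uses t(0.95, n − 1). Solving for 80% power:

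| n | two-sided 5% | one-sided 5% |
|---|---|---|
| 20 | d = 0.66 | d = 0.58 |
| 25 | d = 0.58 | d = 0.51 |

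Both columns are needed because the sample size section uses both terms. The table holds for whichever difference is tested, so the power claim does not reveal which one was meant.

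**2. The null tested as written.** Suppose the pair is visit 1 and visit 4 on the laser side, and the laser adds nothing. The mean change then equals the cysteamine effect, d SDs of within-side change. The protocol gives no value for d, so the values below are assumptions. Noncentrality at n = 20 is d × √20 = d × 4.472.

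| assumed d | noncentrality, n = 20 | rejection, n = 20, two-sided 5% | rejection, n = 25, two-sided 5% | rejection, n = 20, one-sided 5% |
|---|---|---|---|---|
| 0.3 | 1.34 | 25% | 30% | 36% |
| 0.5 | 2.24 | 56% | 67% | 70% |
| 0.8 | 3.58 | 92% | 97% | 96% |

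**3. The same situation tested between sides.** With no laser effect, the expected difference between sides is zero whatever cysteamine does. The two-sided 5% test rejects in 5% of trials, 2.5% in favour of the laser. A simulation (40,000 trials, n = 20, between-side correlation 0.5 or 0.9) gave 2.4% to 2.6% in favour of the laser for d from 0.2 to 0.8.

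**4. Whether a side-specific score is available.** In the mMASI table each malar area scores up to 0.3 × 6 × 4 = 7.2, and left and right are scored separately. Forehead (0.3 × 6 × 4 = 7.2) and chin (0.1 × 6 × 4 = 2.4) are not split by side. Together they make 9.6 of 24 points, or 40% of the range. A malar-only contrast uses the other 14.4 points.

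**5. Timing.** The visit schedule lists melasma grading at visits 1 and 4 (week 12) and none at visits 2 and 3. The in-person endpoint names week 4, so it does not match the grading schedule.

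**The case against.** The strongest reply is that the comparison is already fixed. The aim, objective, research hypothesis and random choice of side all state it. A paired t-test is the natural test for a split face, and its one-sided form suits a directional hypothesis. A between-side contrast of changes is itself built from before-after changes, so the design label may be incomplete rather than wrong. On this reading the null is only loosely worded.

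Much of this stands. A reader might infer that the trial is sized for, and will test, a different question from its objective. The documents do not support that: the pair is unnamed and may be the two sides, in which case none of the before-after percentages apply. A reader might also infer that 20 subjects are too few for the between-side question. That is not supported either, because no between-side difference or SD is given.

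The reply does not remove the defect. The power statement is tied to the formal null, not to the research hypothesis, and nothing states a between-side pairing. Allowing a more powerful final model changes the model, not the null. A separate analysis plan could name the pair, but it would then either carry out a null without a comparator or depart from the protocol's stated one.

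**Conclusion.** The point holds as a defect of statement that should be corrected. The formal null names no comparator, the pair is undefined, and the design label and whole-face endpoint do not express the randomised comparison in the objective. That the test itself addresses the wrong question is possible but not established.

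The size is conditional. On the before-after reading, with no laser effect, n = 20 and two-sided 5%, the null is rejected in 25%, 56% or 92% of trials for assumed cysteamine-only changes of 0.3, 0.5 or 0.8 SD, against 2.5% in favour of the laser for a between-side test. If the two sides are the pair, the test can answer the objective, and the fault lies in the wording of the null, label and endpoint.

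**What to change.** - **Statistical Hypothesis:** restate the null as no within-patient difference between the laser-plus-cysteamine side and the cysteamine-only side in mean change from baseline to week 12 in a side-specific mMASI.
- **Sample Size Calculation:** name the two sides of one face as the pair and reconcile one-sided with two-sided. State that 20 subjects give 80% power only for a between-side difference of about 0.66 SD of the paired differences (two-sided 5%) or 0.58 SD (one-sided 5%). This says what n = 20 can detect, not that such an effect is expected.
- **Study Design:** relabel as randomised split-face, within-patient controlled.
- **Criteria of Evaluation:** define the mMASI endpoint per side and reconcile its week 4 with the week 12 grading at visit 4.
- Keep the before-after change on each side as descriptive.

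Preferably, the side-specific score grades each half of the forehead and chin as well as the malar areas, at the existing visit 1 and visit 4 gradings. A malar-only score is a fallback: it omits 40% of the range and gets no information from subjects without malar melasma, who are eligible because inclusion requires only visible facial melasma.

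The cost is text edits in four places and slightly more grading work, with no extra subjects or visits. The stated detectable difference may look less favourable than a bare claim of 80% power.

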#### Sample Size Calculation:

A sample size is calculated to test the null hypothesis with a one-sided paired t-test for simplicity, although the final analysis may employ a statistically more powerful model.

We calculate that for a two-sided alpha level of 5%, a sample size of 20 subjects will enable us to test the null hypothesis with 80% power. In order to enable the analysis and take into account the potential for dropout we may include up to 25 patients.

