### Procedure:

#### Visit 1 (Screening and Initial Treatment Visit)

- Verify that subject is qualified to participate in the study.
- Ask subject to give personal information, such as name, date of birth, race and ethnicity.
- Review medical and dermatology (skin) history, including history of previous treatments to area being treated.
- Review past and current medications and skin care products.
- See how tall subject is and how much subject weighs
- If subject is a woman and can have children, urine will be tested to see if subject is pregnant. The study doctor or study staff will tell subject if pregnancy test results are positive. The results of the pregnancy testing must be negative in order for subject to be in the study.
- Supply patient with topical cysteamine cream and review instructions for its use
- Identify and examine the area (i.e, side) of face to which the Diode 1927 nm laser will be used (mapping)
- Take photos of face
- Perform grading of melasma
- Perform treatment according to guidelines stated in protocol
- Schedule the next study visit

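### The protocol sizes the trial on a paired t-test but leaves the final model unnamed and optional, with no commitment to fix it before data are seen

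*Protocol*

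**What the plan says.** All of the protocol's statements about the test stand under Sample Size Calculation:

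- The basis of the sample size and the final analysis: a "one-sided paired t-test for simplicity, although the final analysis may employ a statistically more powerful model". The model, its covariates and the time at which it is chosen are not given.
- The level and size: "for a two-sided alpha level of 5%, a sample size of 20 subjects" "will enable us to test the null hypothesis with 80% power". The test is one-sided in one sentence and the alpha two-sided in the next.

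Elsewhere, the Background states the primary objective as laser plus cysteamine against cysteamine alone: "This efficacy will be assessed using modified Melasma Area and Severity Index (mMASI) scores". The Study population paragraph randomises one side of the face to laser. Visit 1 lists "Perform grading of melasma", and Visit 4 (week 12) lists the same step. Criteria of Evaluation (Study Endpoints) gives change in mMASI as a clinical endpoint but names no test.

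**The concern.** The sentence does more than stay silent. It calls the t-test a simplification, says that a more powerful model may be used, and makes that use optional. On the protocol's wording, an analyst could fit both and let the result decide which to report. The nominal 5% level holds for each test alone but not for the better of the two.

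The surrounding text does not narrow the choice. The null hypothesis under Statistical Hypothesis mentions no comparison between sides, the design is labelled before-after, and the sidedness of the test is stated in two ways.

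Precision is also at stake. In a randomised-side design, a t-test on change subtracts the whole baseline side difference, measurement error included. Regression on the baseline difference subtracts only the part that predicts the outcome. With 20 pairs this can matter, and nothing commits the sponsor to it.

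**Working it through.** **Inputs.** From the protocol: n = 20, 80% power, 5% alpha, paired t-test. Assumed, because the protocol gives no effect size, SD or correlation: normal side differences, correlation r between the baseline and week-12 side differences, and (except in step 4) equal SDs at the two times.

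**1. The protocol's own figure.** Without an effect size, 20 subjects at 80% power can be neither confirmed nor refuted. Solving the noncentral-t power function (19 df) for the standardised paired effect dz gives:

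- two-sided 5%: dz = 0.66;
- one-sided 5%: dz = 0.58.

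The sidedness conflict therefore matters. If 0.58 was meant, two-sided power at n = 20 is 69% and 26 subjects are needed. If 0.66 was meant, one-sided power is 89% and 16 suffice. The two-sided dz = 0.66 is the reference below.

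**2. Type I error if the test is picked afterwards.** 40,000 null trials of n = 20 were simulated for each r in the table:

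| r | change-score t-test | baseline-adjusted | smaller p of the two |
|---|---|---|---|
| 0.3 | 5.1% | 5.1% | 8.0% |
| 0.5 | 5.0% | 5.1% | 7.4% |
| 0.7 | 4.9% | 5.0% | 6.8% |

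At r = 0.9-0.95 the smaller-p rule gives about 6%. Simulation error is about 0.1 percentage point: √(0.08 × 0.92 / 40,000) = 0.0014. Adding a t-test on week-12 scores alone as a third candidate gives about 9.5-10.1% at r = 0.3-0.7.

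**3. Precision with equal SDs.** With the side-difference variance set to 1, the change score has variance 2(1 − r) and the adjusted residual has 1 − r². Their ratio is (1 + r)/2 in large samples. Estimating the slope multiplies this by (n − 2)/(n − 3) = 18/17 = 1.059.

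| r | (1 + r)/2 | × 18/17 | adjusted power where change-score t-test has 80% |
|---|---|---|---|
| 0.3 | 0.65 | 0.69 | 92% |
| 0.5 | 0.75 | 0.79 | 88% |
| 0.7 | 0.85 | 0.90 | 84% |
| 0.9 | 0.95 | 1.01 | about 80% |
| 0.95 | 0.975 | 1.03 | about 79% |

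Powers are from simulation at n = 20.

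**4. Unequal SDs.** With the week-12 SD equal to k times the baseline SD, the ratio is k²(1 − r²) × (18/17) / (1 + k² − 2rk). At k = 1.2 and r = 0.7:

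- numerator: 1.44 × 0.51 × 1.059 = 0.778;
- denominator: 1 + 1.44 − 1.68 = 0.76;
- ratio: 1.02, with power about 79%.

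At k = 0.8 and r = 0.7 the ratio is 0.64 × 0.51 × 1.059 / (1 + 0.64 − 1.12) = 0.346/0.52 = 0.66, a larger gain than with equal SDs.

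**5. Can a side difference be formed?** The mMASI table adds one forehead, one left malar, one right malar and one chin score, weighted 0.3, 0.3, 0.3 and 0.1. Only the malar areas are scored by side. The forehead and chin weights (0.3 + 0.1 = 0.4 of 1.0) have no side, and the visit lists do not say that grading is done per side. Any between-side analysis, the paired t-test included, needs a per-side score that the protocol does not yet define.

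**The case against.** The strongest reply is that the final model belongs in the statistical analysis plan, which is not shown. Sizing a trial on a simple test while expecting a more efficient model is ordinary practice. This stands to the extent that a missing model is not in itself a fault of the protocol, and nothing says that two tests will be run. It does not cover the wording: the clause makes the model optional and neither refers the choice to a later plan nor requires it to be fixed before data are seen.

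A reader might also infer that baseline severity will go unused. The protocol does not support that. The t-test is stated for the sample size, the endpoint is change in mMASI (which already subtracts baseline), and the open clause would permit a baseline-adjusted model.

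A third reply is that a paired t-test on between-side change is valid and that adjustment does not always help with 20 pairs. Both are true, as steps 3 and 4 show. The preference for regression is one of expected efficiency, not of validity. It does not bear on the need to name one analysis.

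**Conclusion.** The point holds for the discretionary clause. The protocol names one test, for the sample size only, and keeps an unnamed alternative available with no commitment made before the data. The type I error of about 6-8% is conditional: it arises only if the choice follows the results, and it rests on normal scores, equal SDs and r from 0.3 to 0.95. It is not a prediction of what the sponsor will do, and an analysis plan fixed beforehand would remove it.

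The efficiency gain is likely but not assured. Power rises from 80% to between 84% and 92% for r from 0.7 down to 0.3 with equal SDs. There is no gain, or a loss of 1-2 points, if r is about 0.9 or above or the week-12 SD is somewhat larger than baseline. The point does not invalidate the trial, but it should be settled before any outcome data are seen.

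**What to change.** Replace the open clause with one named primary analysis, fixed before data are seen:

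- **Primary:** linear regression of the week-12 between-side mMASI difference (laser plus cysteamine side minus cysteamine-only side) on the baseline between-side difference. The intercept is the laser effect, tested at two-sided 5% and reported with a 95% CI.
- **Sensitivity only:** the paired t-test on between-side change.
- **Per-side score:** state which is used, for example the side-specific malar scores, or forehead and chin graded by half.
- **Sidedness:** make the one-sided and two-sided wording under Sample Size Calculation agree.
- **Time point:** the endpoint list gives the in-person mMASI change to week 4, while grading is scheduled at Visits 1 and 4. Reconcile these so that week 12 is stated consistently.

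The cost is a few sentences and one degree of freedom. Malar scores alone need no new measurement beyond the existing table but drop the forehead and chin. Grading those by half changes the grading form at both visits and must be in place before the first subject is graded.

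### The 80% power at 20 patients has unclear sidedness and no stated inputs, and cannot be tied to the laser-plus-cysteamine versus cysteamine-alone comparison

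*Protocol*

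**What the plan says.** **Test and alpha.** Under Sample Size Calculation the protocol first says: "A sample size is calculated to test the null hypothesis with a one-sided paired t-test for simplicity". The next sentence claims that "for a two-sided alpha level of 5%, a sample size of 20 subjects will enable us to test the null hypothesis with 80% power". Up to 25 patients may be included to allow for dropout. No mean difference, SD, correlation or standardised effect is given there or elsewhere.

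**Null and design label.** The null under Statistical Hypothesis reads "Treatment of melasma on face with Clear & Brilliant laser and topical cysteamine will not lead to significant improvement". The Study Design line reads "Single Center, Prospective, With Before-After Analysis".

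**The question asked.** The primary objective, in the Background, is the efficacy of the combination "compared to topical cysteamine alone in the treatment of melasma". Every patient gets cysteamine, and under Study population "one side of the face will be randomly selected for treatment with laser". The first listed hypothesis expects both sides to improve, with more improvement on the laser side.

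**The variable and its timing.** The Background plans mMASI "at baseline and at follow up visits at week 4, 8 and 12", and the first hypothesis uses the same three weeks. Study population says "Subject improvement will be assessed via investigator and subject grading at visit 1 and 4". The Procedure lists agree with that: melasma grading appears at Visit 1 and Visit 4 (week 12) and not at Visits 2 and 3. The Clinical Endpoints put the in-person mMASI change at week 4.

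**The concern.** The 80% figure is the only justification offered for 20 patients, and it can be read in more than one way.

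- The sidedness of the test and of the alpha disagree in adjacent sentences.
- A paired t-test fits a baseline-to-follow-up change on one side as well as a side-to-side difference, so naming the test does not show which was powered.
- The written null could be rejected by a change that cysteamine alone produces, since improvement is expected on both sides. Such a result would not show that laser adds anything.

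The SD of a change on one side is also not the SD of a between-side difference, so a calculation made for one does not carry over to the other. What is at stake is whether the sponsor can later say that the comparison it reports is the one it planned and powered.

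**Working it through.** **Inputs from the protocol.** n = 20 pairs, power 80%, alpha 5% stated as two-sided, test stated as a one-sided paired t-test, up to 25 enrolled. The difference and SD are not stated.

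**Reproducing the plan's figure.** This is not possible without an effect size. What can be done is to solve for the standardised paired difference d = (mean paired difference)/(SD of paired difference) that 20 pairs would detect.

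**Formula.** Power = P(T > t_crit), where T is noncentral t with n − 1 degrees of freedom and noncentrality d√n. The lower tail is added for a two-sided test.

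| n | Test | t_crit | d for 80% power |
|---|---|---|---|
| 20 | two-sided 5% | 2.093 | 0.660 |
| 20 | one-sided 2.5% | 2.093 | 0.660 |
| 20 | one-sided 5% | 1.729 | 0.577 |
| 25 | two-sided 5% | 2.064 | 0.584 |

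**Effect of the sidedness clash.**
- If 20 was derived at two-sided 5% or one-sided 2.5%, a two-sided 5% test keeps its 80% power.
- If 20 was derived at one-sided 5% (d = 0.577), a two-sided 5% test has 68.7% power with 20 pairs (noncentrality 0.577 × √20 = 2.58) and 79.0% with 25.

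**Why the choice of comparison matters.** With equal SDs on the two sides and correlation ρ between their changes, SD(between-side difference) = SD(per-side change) × √(2(1 − ρ)). The protocol gives no ρ, so these values are assumptions:
- ρ = 0: factor 1.414, so 0.660 SD of the difference is 0.93 SD of the per-side change.
- ρ = 0.5: factor 1.000, giving 0.66.
- ρ = 0.8: factor 0.632, giving 0.42.

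**Can mMASI be split by side?** In the mMASI table each malar area contributes at most 0.3 × 6 × 4 = 7.2 points and is scored left and right. Forehead and chin together contribute (0.3 + 0.1) × 6 × 4 = 9.6 of 24 points and have one score each, so they cannot be assigned to a side.

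**The case against.** The case against has several sound parts.

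- **No arithmetic error is shown.** One-sided 2.5% and two-sided 5% are the same requirement, and the sentence that gives 20 says two-sided. The wording may be a harmless slip. This stands: the 69% figure depends on a derivation that the protocol does not state.
- **The null is vague rather than demonstrably wrong.** It names no comparator, but it does not say change from baseline either. The Background, the hypotheses and the randomised side all supply the comparator, and a paired t-test suits it. A reader might infer that the trial was powered for the wrong comparison. The text supports only that the powered comparison is ambiguous.
- **The null matches other parts of the protocol.** The Protocol Summary purpose, the later Purpose section and Objective A also speak of the combination without a cysteamine-only comparator. This stands, and it means that editing the null alone would leave the inconsistency in place.
- **Week 4 in the Clinical Endpoints is probably a slip for visit 4.** The rest of that section uses visit 4 and week 12. This is the likelier reading, so it should not be taken as a deliberate competing time point.

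The missing difference and SD would, on their own, be missing detail. What remains is that the null as worded does not answer the stated primary objective, and that the sidedness contradicts itself.

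**Conclusion.** The point holds as one of ambiguity and should be corrected. The stated power cannot be checked, its sidedness is contradictory, and the null as written can be rejected without any evidence that laser adds to cysteamine.

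In size, 20 pairs give 80% power for 0.66 SD of the paired difference at two-sided 5%, or 0.58 SD at one-sided 5%. The possible loss, to 69%, arises only if 20 was derived at one-sided 5% and the analysis is two-sided at 5%.

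A reader might go on to conclude that 20 patients are too few. The documents do not support that: with no assumed effect or SD, the sample size can be shown neither adequate nor inadequate. The figures rest on the paired t-test that the protocol names and on complete pairs.

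**What to change.** 1. **Null and design.** Under Statistical Hypothesis write: *no difference in mean change in mMASI from baseline to week 12 between the laser-plus-cysteamine side and the cysteamine-only side*. Name which mMASI rating in the Clinical Endpoints is primary. The blinded photographic rating is already planned and guards against bias from a treating physician who knows which side had laser. Relabel the Study Design as a randomised split-face (within-subject) comparison, and align the Protocol Summary purpose, the Purpose section and Objective A with it.
2. **Sample size.** Delete the word one-sided. State that 20 evaluable patients give 80% power, with a two-sided paired t-test at 5%, for 0.66 SD of the between-side difference (0.58 SD if 25 complete). Give the assumed difference and SD. If there were none, say that the number was set by feasibility and that 0.66 SD is back-calculated, so it describes the sample size and does not justify it.
3. **Time point.** Correct week 4 in the Clinical Endpoints. Week 12 is the only post-baseline visit with scheduled grading. For weeks 4 and 8 in the Background and hypotheses, there are three options: delete them, score the photographs that the visit lists already include, or add grading. If kept, they should be secondary.
4. **Score.** Compare a side-attributable mMASI score, for example left versus right malar, which the table already separates. Note that this omits 9.6 of 24 points. Scoring forehead and chin by side is the alternative. Both depart from the validated total.

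**Cost.** This is mainly rewording, with no change to the enrolment target. The malar score needs no new assessment. Scoring forehead and chin by side, scoring the week 4 and 8 photographs, or adding grading at those visits each adds rating work. The power statement will read less favourably once it is tied to 0.66 SD.
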